19.3 METHODS FOR HANDLING MISSING DATA

No replacement or imputation of missing data will be conducted for this study.

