All patients on drug treatment will enter a 2-week wash-out and safety follow up period following end of the Treatment Period with procedures conducted according to the Schedule of Events (See [Appendix 1](#)).

Patients with a Worst Itch NRS score less than 5 (< 5) enter the Observation Period:

Patients with a Worst Itch NRS score < 5 at Visit 1a will enter into an extended screening period, Observation Period (no drug treatment), of the study and will be followed for up to 12 weeks (extended screening weeks). Visit 1a for these patients is also Observational Visit 1 (OV1). Subsequent visits will be defined as OV2, OV3 and OV4 and will occur at approximately monthly intervals for the next 3 months.

During this Observation period, patients who report an increase in their Worst Itch NRS with a score of ≥ 5 at any one of their Observation Visits and meet all other eligibility criteria will be able to enroll immediately into the Treatment Period of the study and Visit 1b procedures are to be performed. Patients will receive open-label Study Drug starting with an evening 30 mg dose (to be taken at home), after the Visit 1b procedures have been completed. Receipt of the first drug will indicate the start of their Treatment Period and enrollment into the study. The duration of the Treatment Period for such a patient will vary depending upon the visit at which they transition from the Observation Period to the Treatment Period.

Patients in the Observation Period whose Worst Itch NRS score remains <5 over the 12 extended screening weeks will be screen failed from the study at the end of that time period.

Failure to Improve Criteria:

Beginning on TV 3 and at every subsequent Treatment Visit, patients with a Worst itch NRS equal to or greater than (\geq) the Worst Itch NRS at Visit 1a (or at Visit 1b in the case of patient who require the Observation Visit period) will be discontinued from taking study drug. Subjects discontinued from taking study drug are to undergo the End of Treatment Visit (TV14), the Washout/Safety Follow-up Period assessment in two weeks and receive a follow-up Telephone Contact 30 days following end of study drug for final safety

	assessment.

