	
Treatment Period after participating in the Observation Period for any length of time.
 
 • Assess skin lesion improvement using the metrics of the PAS • Change from Baseline in Patient-Reported Outcome measures Worst itch NRS, average itch intensity NRS, VRS (itchy, burning and stinging), MOS Sleep-R, ItchyQoL, HADS) by Treatment Period study visit and Baseline NRS score • Change between Baseline and final Treatment Period visit in PBI-P • A description of the percentage of patients utilizing various doses of nalbuphine HCl ER tablets by Study Week • A description of the frequency and reasons for dose up- and down-titration and treatment discontinuation during the study • Frequency and distribution by time on study of patients determined to meet failure to improve criteria • Changes in the PRO measurements during the Washout Period after cessation of treatment of nalbuphine HCl ER tablets • Time to the first use of rescue medications and the number of days of use of rescue medications for itching • To evaluate the daily changes in the Subjective Opiate Withdrawal Scale (SOWS) during the Washout Period after cessation of treatment of nalbuphine HCl ER tablets 
Exploratory Endpoint
 
 • Impact on the measurement of nerve fiber density (histology) and MOR/KOR density (histology, Western Blot), as well as histological (H&E) changes in skin biopsies taken at Baseline and the final Treatment Period Visit to investigate possible correlation with any clinical response and also compared to biopsy material assessed during study TR03 (optional procedures at select sites only).

Statistical Methodology
	
Efficacy:
 
All efficacy endpoints will be evaluated through the generation of summary statistics. For continuous variables, the mean, standard deviation, median, minimum, and

maximum will be presented for a particular visit and for the change from baseline (Visit 1a or 1b). For categorical variables, the number and percentage of patients within each category of classification will be summarized by study visit. No formal statistical testing will be conducted.

Safety:

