5.2 SECONDARY ENDPOINTS

Visit 1a or 1b will serve as the baseline visit for efficacy endpoints. Visit 1a will be the baseline for patients directly entering the Treatment Period as of Visit 1a. Visit 1b will be the baseline for patients entering the Treatment Period after participating in the Observation Period for any length of time.

- Assess skin lesion improvement using the metrics of the PAS
- Change from Baseline in Patient-Reported Outcome measures Worst itch NRS, average itch intensity NRS, VRS (itchy, burning and stinging), MOS Sleep-R, ItchyQoL, HADS) by Treatment Period study visit and Baseline NRS score
- Change between Baseline and the final Treatment Period visit in PBI-P
- A description of the percentage of patients utilizing various doses of nalbuphine HCl ER tablets by Study Week
- A description of the frequency and reasons for dose up- and down-titration and treatment discontinuation during the study
- Frequency and distribution by time on study of patients determined to meet failure-to-improve criteria
- Changes in the PRO measurements during the Washout Period after cessation of treatment of nalbuphine HCl ER tablets
- Time to first use of rescue medications and the number of days of use of rescue medications for itching
- To evaluate the daily changes in the Subjective Opiate Withdrawal Scale (SOWS) during the Washout Period after cessation of treatment of nalbuphine HCl ER tablets.

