9.6.2.2.1 TV 3 (Treatment Week 5)

The following procedures are to take place at this visit:

- Administer the Worst Itch NRS and evaluate against the Failure-to-Improve criteria (see [Section 11.1](#))
- For patients who MEET the Failure-to Improve criteria
 - Stop study medication
 - Perform End of Treatment Visit (TV14) procedures
- For patients who DO NOT meet Failure-to-Improve criteria, perform the following procedures
 - obtain vital signs
 - collect urine for pregnancy test (must be confirmed negative prior to dispensing study drug)
 - collect blood for PK
 - perform 12-Lead ECG after at least 5 minutes in a supine position (See the Study Reference Manual for ECG procedures, [section 17.4](#) Electrocardiograms for the handling of Cardiovascular adverse events)
 - perform brief neurological assessment
 - administer PRO measurements:
 - Average itch intensity NRS

- VRS
- ItchyQoL
- MOS Sleep-R
- HADS

The PRO questionnaires must be administered at the study site under the supervision of and by trained study staff, strictly adhering to PRO Administration Instructions (see Study Reference Manual).

- record AEs
- review of concomitant medications, including over-the-counter medications, nutritional supplements, and vitamins
- reinforce compliance
- perform study drug accountability, retrieve previously dispensed study drug
- dispense the study drug to the patient required until the next Treatment Visit

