⁶ Beginning on TV 3 and at every subsequent Treatment Visit, patients with a Worst itch NRS \geq the Worst itch NRS at Visit 1a (or at Visit 1b in the case of patient who require the OV period) will be discontinued from study drug, complete the End of Treatment Visit 14, the Washout and Safety Follow-up Period and Visit, and a Telephone Contact Visit 30 days after the last dose of study drug.

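### The failure-to-improve rule decides who is left to be summarised, so by-visit means (Worst Itch from TV4, other PROs from TV3) overstate benefit, and the TV14 summary mixes time points

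*Protocol*

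**What the plan says.** All references are to the amended protocol (Version 2.0) unless noted.

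- **The rule (Synopsis, Failure to Improve Criteria; Table 3, footnote 6).** "Beginning on TV 3 and at every subsequent Treatment Visit, patients with a Worst itch NRS equal to or greater than" the patient's own Visit 1a or 1b score "will be discontinued from taking study drug". A tie with baseline counts as failure.
- **Order of assessment (9.6.2.2.1 to 9.6.2.2.11, TV3 to TV13).** Worst Itch NRS is given first, to every attender, and checked against the rule. Patients who fail stop drug and do the TV14 procedures instead.
- **Other assessments at those visits.** Average itch NRS, VRS, ItchyQoL, MOS Sleep-R and HADS are listed after the line "For patients who DO NOT meet Failure-to-Improve criteria, perform the following procedures" (wording at TV3, near-identical at later visits). At TV8 the PAS is on that list too.
- **TV14 (9.6.2.2.12).** It covers patients who finish treatment and also those who met the rule at any earlier Treatment Visit. For direct entrants who finish, it falls in Week 51.
- **Endpoints.** Section 5.2 asks for PRO change from baseline "by Treatment Period study visit and Baseline NRS score". Section 4.2 asks for change by the final Treatment Period visit. The Synopsis specifies descriptive statistics per visit and for change from baseline, with no formal testing.
- **Disclosure of stops.** Section 5.2 makes the frequency and timing of failures a secondary endpoint.

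**The concern.** The scale being summarised is also the scale that decides who remains to be summarised. Once a patient has scored at or above baseline at TV3 or later, no further on-treatment scores from that patient enter the by-visit means. Those who remain have been below baseline at every earlier check. With ordinary visit-to-visit variation, that selection alone produces a negative mean change that deepens over successive visits, even if the drug does nothing.

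The study has no control arm, so nothing else in it would reveal the artefact. Its title names anti-pruritic efficacy, and a reader would take a by-visit table of this kind as evidence of sustained and growing itch relief. TV14 has a different fault: it presents scores taken anywhere from Week 5 to Week 51 as one time point.

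**Working it through.** The plan gives no figure to reproduce; it has no sample size calculation, power or alpha. The check is therefore a simulation of the rule as written.

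**From the protocol:** integer NRS 0 to 10; entry at Worst Itch 5 or more; rule applied at 11 visits (TV3 to TV13); failure when the score is at or above baseline.

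**Assumed, not in the protocol:** true itch mean 6.5, between-patient SD 2, visit-to-visit SD 1.5 (also 0.5), true effect 0 or 2 points. Each score is the patient's true level plus effect plus visit noise, rounded and clipped to 0 to 10. Hundreds of thousands of patients were simulated per scenario; results move by about 0.01 to 0.02 between runs.

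**Quantities.** Let c(k) be the score at visit k minus baseline.

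- Rule: stop at the first k from TV3 with c(k) >= 0. Anyone who passes has c(k) <= -1.
- By-visit display: mean of c(k) among attenders, i.e. those with c <= -1 at every check before k. Patients failing at visit k itself are included.
- Reference: mean of c(k) in the same cohort followed without the rule.

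**Worst Itch by visit**

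| Scenario | Visit | Attenders | No rule | Bias |
|---|---|---|---|---|
| No effect, visit SD 1.5 | TV3 | -0.34 | -0.34 | 0 |
| No effect, visit SD 1.5 | TV4 | -1.08 | -0.34 | -1.08 + 0.34 = -0.74 |
| No effect, visit SD 1.5 | TV13 | -2.61 | -0.34 | -2.61 + 0.34 = -2.27 |
| 2-point effect, visit SD 0.5 | TV13 | -2.14 | -2.01 | -2.14 + 2.01 = -0.13 |

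The no-rule -0.34 is regression to the mean from selecting a baseline of 5 or more.

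If failing scores were also dropped from their own visit, the no-effect figures would be -2.05 at TV3 (44.5% left) and -2.94 at TV13 (4.7% left).

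**A second set of assumptions** (true mean 7 to 8, between-patient SD 1 to 1.5, visit SD 1 to 2, no effect) gives -0.7 to -1.2 at TV4 and -1.8 to -3.0 at TV13 among attenders. Average Itch at TV3, taken only from patients who pass, is -1.0 to -1.6, against +0.01 to -0.15 without the rule. That figure also assumes a 0.7 correlation between the noise in worst and average itch.

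**TV14, failures and completers pooled**

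| Scenario | Pooled | TV14 without the rule |
|---|---|---|
| Constant 2-point effect, visit SD 1.5 | -0.89 | -2.24 |
| Constant 2-point effect, visit SD 0.5 | -1.85 | -2.01 |
| Effect drifting from -2 to +2, visit SD 1.5 | +0.49 | +1.25 |

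Under a constant effect the pooled value understates benefit, because failures are caught on an upward fluctuation. When benefit wanes and itch then worsens, the pooled value looks better than the truth, because failures leave before the worst scores.

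**The case against.** **By-visit values are not all negative by construction.** A reader might infer that every by-visit mean must show improvement, TV3 Worst Itch included. The text does not support that. Worst Itch is taken from all attenders before the rule is applied, and nothing says the failing score is removed from its visit. With failing scores kept, TV3 Worst Itch equals the no-rule value. The certainty applies only to Worst Itch among patients who pass; for the other PROs the selection works through correlation. This stands, but it rescues only TV3: later visits have already lost earlier failures.

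**The final visit is not necessarily biased the opposite way.** A reader might also infer that the TV14 summary always understates benefit. It does so under a constant effect but can reverse, and the pooled value is a legitimate last-on-treatment score. What remains is that Week 5 and Week 51 scores are presented as one time point.

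**The missing-data sentence is superseded.** The statement "No replacement or imputation of missing data will be conducted for this study" is in Version 1.0, which had no failure-to-improve rule. Version 2.0's Sections 11.1 and 19 are not in the text at hand, so the point must not rest on that sentence. It does not: the rule, the restricted assessment lists, the TV14 pooling and the by-visit endpoint are all in the visible Version 2.0 text.

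**The selection is disclosed, and little hangs on it.** Failure counts are a secondary endpoint, so a null drug's TV13 mean would sit beside a report that about 95% had stopped (4.7% of 60 is about 3 patients). Disclosure helps but does not correct the mean. The primary endpoint is safety, efficacy is descriptive, and Section 9.2 singles out PAS lesion improvement as the important secondary endpoint. This lowers the severity.

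**Conclusion.** The concern holds in this form. Observed change-from-baseline means overstate benefit from TV4 for Worst Itch and from TV3 for the other PROs, because earlier failures (and, for the other PROs, same-day failures) are absent.

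The size depends on visit-to-visit variation and the true effect, neither of which the protocol gives. In the scenarios above, the TV13 Worst Itch bias runs from about 0.1 point (visit SD 0.5, 2-point effect) to about 2.3 points (visit SD 1.5, no effect). TV3 Worst Itch is unbiased provided failing scores are kept under TV3. The TV14 summary mixes time points; it usually understates benefit under a constant effect, but its direction cannot be relied on.

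This should be fixed, but it is not critical: the affected displays are descriptive secondary endpoints in a safety study, and no test or decision rule depends on them.

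**What to change.** Leave the clinical rule unchanged and alter only the tabulation:

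1. File the triggering Worst Itch score, and the PROs taken that day, under the actual treatment week or nominal visit at which they were collected.
2. Beside each by-visit mean, show the number at risk and the cumulative number stopped, and label the mean as conditional on not having met the rule earlier.
3. At each visit, report the proportion of all treated patients who are still on drug and below baseline, counting stopped patients as not improved.
4. At TV14, report failures and completers separately.

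A repeated-measures model on all on-treatment Worst Itch scores, including the triggering one, can be added as a supportive estimate. Stopping under the rule depends on an observed score, so such a model can account for it. In a simulated cohort of 4,000 with a 2-point effect it gave -2.18, -2.25 and -2.29 at TV3, TV8 and TV13, against true values of -2.18, -2.22 and -2.27. With at most 60 patients it will be much less precise, so it need not be the main estimate.

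The cost is some extra tabulation and a less favourable reported by-visit effect. No new data, visits or patients are needed.

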9.6.2.2.2 TV 4 (Treatment Week 9)

The following procedures are to take place at this visit:

- Administer the Worst Itch NRS and evaluate against the Failure-to-Improve criteria (see [Section 11.1](#))
- For patients who MEET the Failure-to Improve criteria
 - Stop study medication
 - Perform End of Treatment Visit (TV14) procedures
- For patients who DO NOT meet Failure-to-Improve perform the following procedures
 - obtain vital signs
 - collect urine for pregnancy test (must be confirmed negative prior to dispensing study drug)
 - collect blood for PK
 - perform 12-Lead ECG after at least 5 minutes in a supine position (See the Study Reference Manual for ECG procedures, [section 17.4](#) Electrocardiograms for the handling of Cardiovascular adverse events)
 - perform brief neurological assessment
 - administer PRO measurements:
 - Average itch intensity NRS
 - VRS
 - ItchyQoL
 - MOS Sleep-R
 - HADS

The PRO questionnaires must be administered at the study site under the supervision of and by trained study staff, strictly adhering to PRO Administration Instructions (see Study Reference Manual).

- record AEs
- review of concomitant medications, including over-the-counter medications, nutritional supplements, and vitamins
- reinforce compliance
- perform study drug accountability, retrieve previously dispensed Study Drug
- dispense study drug required until the patient returns for the next Treatment Visit

9.6.2.2.3 TV 5 (Treatment Week 13)

The following procedures are to take place at this visit:

- Administer the Worst Itch NRS and evaluate against the Failure-to-Improve criteria (see [Section 11.1](#))
- For patients who MEET the Failure-to Improve criteria
 - Stop study medication
 - Perform End of Treatment Visit (TV14) procedures
- For patients who DO NOT meet Failure-to-Improve perform the following procedures
 - obtain vital signs
 - collect urine for pregnancy test (must be confirmed negative prior to dispensing study drug)
 - collect blood for PK
 - perform 12-Lead ECG after at least 5 minutes in a supine position (See the Study Reference Manual for ECG procedures, [section 17.4](#) Electrocardiograms for the handling of Cardiovascular adverse events)
 - perform brief neurological assessment
 - administer PRO measurements:
 - Average itch intensity NRS
 - VRS
 - ItchyQoL
 - MOS Sleep-R
 - HADS

The PRO questionnaires must be administered at the study site under the supervision of and by trained study staff, strictly adhering to PRO Administration Instructions (see Study Reference Manual).

- record AEs
- review of concomitant medications, including over-the-counter medications, nutritional supplements, and vitamins
- reinforce compliance
- perform study drug accountability, retrieve previously dispensed study drug
- dispense the study drug to the patient required until the next Treatment Visit

9.6.2.2.4 TV 6 (Treatment Week 17)

The following procedures are to take place at this visit:

- Administer the Worst Itch NRS and evaluate against the Failure-to-Improve criteria (see [Section 11.1](#))
- For patients who MEET the Failure-to Improve criteria
 - Stop study medication
 - Perform End of Treatment Visit (TV14) procedures
- For patients who DO NOT meet Failure-to-Improve perform the following procedures
 - obtain vital signs
 - collect urine for pregnancy test (must be confirmed negative prior to dispensing study drug)
 - collect blood for PK
 - perform 12-Lead ECG after at least 5 minutes in a supine position (See the Study Reference Manual for ECG procedures, [section 17.4](#) Electrocardiograms for the handling of Cardiovascular adverse events)
 - perform brief neurological assessment
 - administer PRO measurements:
 - Average itch intensity NRS
 - VRS
 - ItchyQoL
 - MOS Sleep-R
 - HADS

The PRO questionnaires must be administered at the study site under the supervision of and by trained study staff, strictly adhering to PRO Administration Instructions (see Study Reference Manual).

- record AEs
- review of concomitant medications, including over-the-counter medications, nutritional supplements, and vitamins
- reinforce compliance
- perform study drug accountability, retrieve previously dispensed study drug
- dispense the study drug to the patient required until the next Treatment Visit

9.6.2.2.5 TV 7 (Treatment Week 21)

The following procedures are to take place at this visit:

- Administer the Worst Itch NRS and evaluate against the Failure-to-Improve criteria (see [Section 11.1](#))
- For patients who MEET the Failure-to Improve criteria

- Stop study medication
- Perform End of Treatment Visit (TV14) procedures
- For patients who DO NOT meet Failure-to-Improve perform the following procedures
 - obtain vital signs
 - collect urine for pregnancy test (must be confirmed negative prior to dispensing study drug)
 - collect blood for PK
 - perform 12-Lead ECG after at least 5 minutes in a supine position (See the Study Reference Manual for ECG procedures, [section 17.4](#) Electrocardiograms for the handling of Cardiovascular adverse events)
 - perform brief neurological assessment
 - administer PRO measurements:
 - Average itch intensity NRS
 - VRS
 - ItchyQoL
 - MOS Sleep-R
 - HADS

The PRO questionnaires must be administered at the study site under the supervision of and by trained study staff, strictly adhering to PRO Administration Instructions (see Study Reference Manual).

- record AEs
- review of concomitant medications, including over-the-counter medications, nutritional supplements, and vitamins
- reinforce compliance
- perform study drug accountability,
- retrieve previously dispensed Study Drug
- dispense the study drug to the patient required until next Treatment Visit

9.6.2.2.6 TV 8 (Treatment Week 26)

The following procedures are to take place at this visit:

- Administer the Worst Itch NRS and evaluate against the Failure-to-Improve criteria (see [Section 11.1](#))
- For patients who MEET the Failure-to Improve criteria
 - Stop study medication
 - Perform End of Treatment Visit (TV14) procedures
- For patients who DO NOT meet Failure-to-Improve perform the following procedures
 - obtain vital signs

- perform physical examination
- perform brief neurological assessment
- complete the PAS
- perform 12-lead ECG after at least 5 minutes in a supine position (See the Study Reference Manual for ECG procedures, [section 17.4](#) Electrocardiograms for the handling of Cardiovascular adverse events)
- collect urine for pregnancy test (must be confirmed negative prior to dispensing study drug)
- collect urine for urinalysis for central lab
- collect blood for central laboratory (hematology and chemistry) and for PK
- administer PRO measurements:
 - Average itch intensity NRS
 - VRS
 - ItchyQoL
 - MOS Sleep-R
 - HADS

The PRO questionnaires must be administered at the study site under the supervision of and by trained study staff, strictly adhering to PRO Administration Instructions (see Study Reference Manual).

- record AEs
- review concomitant medications, including over-the-counter medications, nutritional supplements, and vitamins
- reinforce compliance
- perform study drug accountability, retrieve previously dispensed study drug
- dispense study drug to the patient required until the next Treatment Visit

